Appendix 3 Sample Diary Card

Please assess your symptoms and complete this form each evening (after 4 pm)

Day	Date	Oral Temp (°F)	Systemic Events							Local Reactions (at the Injection Site)				
			Headache (0 to 3)	Chills (0 to 3)	Fatigue (0 to 3)	Nausea (0 to 3)	Diarrhea (0 to 3)	Vomiting (0 to 3)	Muscle Aches (0 to 3)	Pain (0 to 3)	Tenderness (0 to 3)	Swelling (0 to 3)	Swelling (size, mm)	Redness (size, mm)
1														
2														
3														
4														
5														
6														
7														
8														

Instructions for Scoring Intensity

Intensity Grading Scale for Systemic Events
 
0 = None 1 = Mild, no interference with daily activity 2 = Moderate, some interference with daily activity 3 = Severe, significant interference, prevents daily activity
	
Intensity Grading Scale for Pain
 
0 = None 1 = Mild, awareness of pain but it does not interfere with daily activity and no pain medication is taken 2 = Moderate, awareness of pain and there is interference with daily activity or requires non-narcotic pain medication 3 = Severe, awareness of pain and it prevents daily activity or requires use of narcotic pain medication
	
Intensity Grading Scale for Tenderness
 
0 = None 1 = Mild, hurts to touch 2 = Moderate, hurts with movement 3 = Severe, significant discomfort at rest
	
Intensity Grading Scale for Swelling
 
0 = None 1 = Mild, does not interfere with daily activity 2 = Moderate, interferes with daily activity 3 = Severe, prevents daily activity

---	--	--	--

Instructions for Measuring Size: Use the ruler provided and record the number of millimeters across the widest part of the red/swelling area.

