2.2.3 Safety Endpoints

- Reactogenicity
 - Local reactions: Pain, tenderness, swelling, redness
 - Systemic events: Fever, headache, chills, fatigue, nausea, vomiting, diarrhea, muscle aches
- AE, SAEs, AESIs, Medically attended AEs (MAAEs)

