7.2.6 Severity

Severity for all AEs, including laboratory abnormalities, will be reported in accordance with Toxicity Grading Scale for Healthy Adult and Adolescent Volunteers Enrolled in Preventive Vaccine Clinical Trials ([Appendix 2](#)).

If an appropriate listing is not present in this table for an AE, the AE will be graded as follows:

- **Grade 1 (Mild)** - No interference with daily activity
- **Grade 2 (Moderate)** - Some interference with daily activity but medical intervention not required (e.g., doctor visit and/or prescription medicine); over-the-counter medicine permitted

- **Grade 3 (Severe)** - Prevents daily activity and requires medical intervention (e.g., doctor visit and/or prescription medicine)
- **Grade 4 (Potentially Life-threatening)** - Emergency room visit or hospitalization

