AE = adverse event; AESI = adverse event of special interest; EQ-5D-5L = EuroQoL – 5 Domains – 5 Levels; MAAE = medically attended adverse event; PBMC = peripheral blood mononuclear cell; SAE = serious adverse event. a At selected sites only b After confirmation of no febrile illness or other acute illness for the past 48 hours and no suspicion of AESI								

Appendix 2 Toxicity Grading Scale for Healthy Adult and Adolescent Volunteers Enrolled in Preventive Vaccine Clinical Trials

Tables for Clinical Abnormalities

Local Reaction to Injectable Product	Mild (Grade 1)	Moderate (Grade 2)	Severe (Grade 3)	Potentially Life-threatening (Grade 4)
Pain	Does not interfere with activity	Repeated use of non-narcotic pain reliever > 24 hours or interferes with activity	Any use of narcotic pain reliever or prevents daily activity	Emergency room (ER) visit or hospitalization
Tenderness	Mild discomfort to touch	Discomfort with movement	Significant discomfort at rest	ER visit or hospitalization
Erythema/Redness	2.5 - 5 cm	5.1 - 10 cm	> 10 cm	Necrosis or exfoliative dermatitis
Induration/Swelling	2.5 - 5 cm and does not interfere with activity	5.1 - 10 cm or interferes with activity	> 10 cm or prevents daily activity	Necrosis

Vital Signs	Mild (Grade 1)	Moderate (Grade 2)	Severe (Grade 3)	Potentially Life-threatening (Grade 4)
Fever (°C) (°F)	38.0 – 38.4 100.4 – 101.1	38.5 – 38.9 101.2 – 102.0	39.0 – 40 102.1 – 104	> 40 > 104
Tachycardia - beats per minute	101 – 115	116 – 130	> 130	ER visit or hospitalization for arrhythmia
Bradycardia - beats per minute	50 – 54	45 – 49	< 45	ER visit or hospitalization for arrhythmia
Hypertension (systolic) - mm Hg	141 – 150	151 – 155	> 155	ER visit or hospitalization for malignant hypertension
Hypertension (diastolic) - mm Hg	91 – 95	96 – 100	> 100	ER visit or hospitalization for malignant hypertension
Hypotension (systolic) – mm Hg	85 – 89	80 – 84	< 80	ER visit or hospitalization for hypotensive shock
Respiratory Rate – breaths per minute	17 – 20	21 – 25	> 25	Intubation

Systemic (General)	Mild (Grade 1)	Moderate (Grade 2)	Severe (Grade 3)	Potentially Life-threatening (Grade 4)
Nausea/vomiting	No interference with activity or 1 - 2 episodes/24 hours	Some interference with activity or > 2 episodes/24 hours	Prevents daily activity, requires outpatient IV hydration	ER visit or hospitalization for hypotensive shock

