Diarrhea	2 - 3 loose stools or < 400 gms/24 hours	4 - 5 stools or 400 - 800 gms/24 hours	6 or more watery stools or > 800 gms/24 hours or requires outpatient IV hydration	ER visit or hospitalization
Headache	No interference with activity	Repeated use of non-narcotic pain reliever > 24 hours or some interference with activity	Significant; any use of narcotic pain reliever or prevents daily activity	ER visit or hospitalization
Fatigue	No interference with activity	Some interference with activity	Significant; prevents daily activity	ER visit or hospitalization
Myalgia	No interference with activity	Some interference with activity	Significant; prevents daily activity	ER visit or hospitalization

Systemic Illness	Mild (Grade 1)	Moderate (Grade 2)	Severe (Grade 3)	Potentially Life-threatening (Grade 4)
Illness or clinical adverse event (as defined according to applicable regulations)	No interference with activity	Some interference with activity not requiring medical intervention	Prevents daily activity and requires medical intervention	ER visit or hospitalization

Tables for Laboratory Abnormalities

Serum	Mild (Grade 1)	Moderate (Grade 2)	Severe (Grade 3)	Potentially Life- threatening (Grade 4)
Sodium – Hyponatremia mEq/L	132 – 134	130 – 131	125 – 129	< 125
Sodium – Hypernatremia mEq/L	144 – 145	146 – 147	148 – 150	> 150
Potassium – Hyperkalemia mEq/L	5.1 – 5.2	5.3 – 5.4	5.5 – 5.6	> 5.6
Potassium – Hypokalemia mEq/L	3.5 – 3.6	3.3 – 3.4	3.1 – 3.2	< 3.1
Glucose – Hypoglycemia mg/dL	65 – 69	55 – 64	45 – 54	< 45
Glucose – Hyperglycemia Fasting – mg/dL Random – mg/dL	100 – 110 110 – 125	111 – 125 126 – 200	>125 >200	Insulin requirements or hyperosmolar coma
Blood Urea Nitrogen BUN mg/dL	23 – 26	27 – 31	> 31	Requires dialysis
Creatinine – mg/dL	1.5 – 1.7	1.8 – 2.0	2.1 – 2.5	> 2.5 or requires dialysis
Calcium – hypocalcemia mg/dL	8.0 – 8.4	7.5 – 7.9	7.0 – 7.4	< 7.0
Calcium – hypercalcemia mg/dL	10.5 – 11.0	11.1 – 11.5	11.6 – 12.0	> 12.0
Magnesium – hypomagnesemia mg/dL	1.3 – 1.5	1.1 – 1.2	0.9 – 1.0	< 0.9
Phosphorus – hypophosphatemia mg/dL	2.3 – 2.5	2.0 – 2.2	1.6 – 1.9	< 1.6
CPK – mg/dL	1.25 – 1.5 x ULN	1.6 – 3.0 x ULN	3.1 – 10 x ULN	> 10 x ULN
Albumin – Hypoalbuminemia g/dL	2.8 – 3.1	2.5 – 2.7	< 2.5	--
Total Protein – Hypoproteinemia g/dL	5.5 – 6.0	5.0 – 5.4	< 5.0	--
Alkaline phosphate – increase by factor	1.1 – 2.0 x ULN	2.1 – 3.0 x ULN	3.1 – 10 x ULN	> 10 x ULN

Serum	Mild (Grade 1)	Moderate (Grade 2)	Severe (Grade 3)	Potentially Life- threatening (Grade 4)

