Any Local Reaction		n (x.x%)	n (x.x%)
Pain		n (x.x%)	n (x.x%)
ETC			

Program:

Date Produced: mm/dd/yy

Programming Notes:

- Information comes from the Diary Card
- If a subject has multiple of the same events, take the maximum severity.
- During the 7 day period after the (Days 1-7) a subject should only be counted one time. If a subject has a sign/symptom at least once during that 7 day interval the subject is counted for that sign/symptom.
- Watch page breaks. Please try and keep all the grades together for a sign/symptom.
- Do not include Grade=0 as Grades of 0 imply "None" or no event.
- Fever is based on Temperature (F) which is collected on the Diary Card. See Appendix 2 in the protocol for grade definitions. Grade 1 = 100.4-101.1; Grade 2 = 101.2-102.0; Grade 3 = 102.1-104; Grade 4 >104.

- For Redness (mm) and Swelling (mm), see also Appendix 2 in the protocol. For both redness and swelling: Grade 1 = 2.5-5 cm; Grade 2 = 5.1-10 cm; Grade 3 = >10cm; Grade 4 is Necrosis or exfoliative dermatitis, which we won't be able to determine and will be handled separately as an AE.

[Sponsor]

Protocol: [Protocol number]

page x of y

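### SAP Table 14.3.1.7 mixes two severity scales in one Grade column: the Diary Card differs from Appendix 2 or Section 7.2.6 for 6 of 12 solicited items, and no row shows the Appendix 2 swelling grade

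*Protocol*

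**What the plan says.** Protocol Section 2.2.3 lists the solicited items: "Local reactions: Pain, tenderness, swelling, redness" and "Systemic events: Fever, headache, chills, fatigue, nausea, vomiting, diarrhea, muscle aches".

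Section 7.2.6 sets the scale: "Severity for all AEs, including laboratory abnormalities, will be reported in accordance with" the toxicity scale in Appendix 2. Events that Appendix 2 does not list fall back on general definitions in the same section, where Grade 3 reads "Prevents daily activity and requires medical intervention (e.g., doctor visit and/or prescription medicine". Section 3.1 repeats the Appendix 2 instruction in the paragraph that introduces the Diary Card.

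The Diary Card (Appendix 3) carries its own 0-to-3 scores. Seven systemic items are scored by interference with activity alone. Pain, tenderness and swelling each have a separate scale, and the swelling scale uses activity only. A pain score of 2 reads "Moderate, awareness of pain and there is interference with daily activity or requires" a non-narcotic analgesic. Temperature, swelling size and redness size are recorded as measurements.

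The programming notes to SAP Table 14.3.1.7 name the card as the data source. They apply Appendix 2 temperature bands to fever and then say "For Redness (mm) and Swelling (mm), see also Appendix 2 in the protocol", listing the size bands. Swelling has two rows, one for the activity score and one for size. Neither document says which scale governs the solicited items or how one converts to the other.

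**The concern.** One Grade column should mean one scale. If the card and Appendix 2 assign different grades to the same event, a Grade 2 or Grade 3 percentage cannot be read without knowing which scale produced it. The Any Local Reaction and Any Systemic Event rows then add up grades of two kinds.

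Swelling raises a more specific problem. The SAP cites Appendix 2 for it but carries over only half of the Appendix 2 definition. Reactogenicity is the first-listed safety endpoint, so readers will look to these rates for the tolerability of the maintenance dose.

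**Working it through.** The documents state no figure on this point, so the check is an item-by-item comparison.

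**Step 1. Items.** 4 local + 8 systemic = 12.

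**Step 2. Compare the scales.** For each item, the criteria that either scale uses were crossed, both scales were applied to each profile, and profiles with different grades were counted.

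- Pain and headache: 3 activity levels × 4 analgesic levels (none, single, repeated, narcotic) = 12.
- Chills: 3 activity levels × medical intervention yes/no = 6.
- Nausea and vomiting: 3 activity levels × 2 episode levels × IV hydration yes/no = 12.
- Diarrhea: 3 activity levels × 3 stool-count bands = 9.

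| Item | Diary Card | Appendix 2 or Section 7.2.6 | Profiles that differ |
|---|---|---|---|
| Pain | Any non-narcotic analgesic gives Grade 2 | Non-narcotic use counts only if repeated beyond 24 hours; Grade 3 is the same | 1 of 12 |
| Headache | Activity only | Repeated analgesic gives Grade 2, narcotic gives Grade 3 | 3 of 12 |
| Chills | Activity prevented gives Grade 3 | Not in Appendix 2; Section 7.2.6 also needs medical intervention for Grade 3 | 1 of 6 |
| Nausea, vomiting | Activity only | Activity or episode count; Grade 3 brings in IV hydration | 4 or 5 of 12 |
| Diarrhea | Activity only | Stool count or weight; Grade 3 is "6 or more watery stools or > 800 gms/24 hours or requires outpatient IV hydration" | 6 of 9 |
| Tenderness, fatigue, muscle aches | Same criteria | Same criteria | 0 of 3 each |
| Fever, redness | Measured | SAP applies Appendix 2 bands | None |

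The range for nausea and vomiting depends on whether the comma in the Appendix 2 Grade 3 text means and (4) or or (5). For chills, activity prevented without medical intervention fails the Section 7.2.6 Grade 3 definition and was coded Grade 2.

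Items that differ: pain, headache, chills, nausea, vomiting, diarrhea = 6. Items that match: 5. Swelling makes 6 + 5 + 1 = 12.

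The direction is mixed. The card is higher for pain Grade 2 and chills Grade 3, and lower for headache. For diarrhea it is lower in 3 of the 6 discordant profiles and higher in 3: six watery stools without interference is Grade 1 on the card and Grade 3 in Appendix 2, while two loose stools that prevent activity is Grade 3 and Grade 1.

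**Step 3. Swelling.** Appendix 2 assigns Grade 2 for 5.1-10 cm or interference, and Grade 3 for more than 10 cm or activity prevented. Each cell shows size row / activity row / Appendix 2 (0 = no grade).

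| Activity | < 2.5 cm | 2.5-5 cm | 5.1-10 cm | > 10 cm |
|---|---|---|---|---|
| No interference | 0 / 1 / 0 | 1 / 1 / 1 | 2 / 1 / 2 | 3 / 1 / 3 |
| Interferes | 0 / 2 / 2 | 1 / 2 / 2 | 2 / 2 / 2 | 3 / 2 / 3 |
| Prevents | 0 / 3 / 3 | 1 / 3 / 3 | 2 / 3 / 3 | 3 / 3 / 3 |

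The size row differs from Appendix 2 in 5 of 12 cells and the activity row in 4 of 12. The higher of the two differs in 1 of 12 (under 2.5 cm without interference) and never in Grade 2-3 status.

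**Step 4. Can a reader rebuild the Appendix 2 rate from the two rows?** Let s and a be the numbers of subjects at or above a given grade (2 or 3) in the size and activity rows, c the number in both, and n the arm size. The Appendix 2 count is s + a − c, anywhere from max(s, a) to min(n, s + a). The table does not print c, so the count cannot be recovered.

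**Step 5. Grade 4.** The table prints Grade 4 rows, but the card scores stop at 3. The SAP notes this gap only for redness and swelling. Fever is the exception, since its Grade 4 follows from the recorded temperature.

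**The case against.** The strongest reply is that Appendix 2 was never meant to govern the card. Section 7.2.6 speaks of AEs. Under Section 6.1, diary events stay off the AE form unless serious. Reactogenicity is analysed apart from AEs in both documents (protocol Sections 10.9.1 and 10.9.2, SAP Sections 12.1 and 12.2), and the card is itself a protocol appendix. This stands to the extent that the card grades cannot be called wrong. But the AE definition in Section 7.2.1 is broad, and Appendix 2 has a table for local injection reactions. The swelling point does not depend on this inference, because the SAP itself invokes Appendix 2 there.

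Second, the Investigator reviews the card, and that assessment is also source. True, but no regrading rule is given.

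Third, the swelling split can be called layout: the higher row gives the right Grade 2-3 status, and a maximum-severity Any Local Reaction row could recover it. That holds for the Any row if it is built over both swelling rows, which the SAP does not say. It does not hold for the swelling rate itself (Step 4).

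Fourth, nausea is the thinnest of the six. Appendix 2 does use interference for it, so without vomiting Grades 1-2 agree on that criterion and the conflict sits in Grade 3. It remains on either reading of the comma, at different profiles.

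**Conclusion.** The point holds as a correction of minor weight. Card grading differs from Appendix 2 or Section 7.2.6 for 6 of 12 items, one Grade column mixes the scales, and no row reports the Appendix 2 swelling grade. The profile counts show where grades can differ, not how often. The documents give no frequencies from which to estimate the number of subjects affected.

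A reader might infer more than this, and the documents do not support it:

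- **That the Grade 2-3 rates as a whole are off scale, or that swelling is a seventh contradiction in wording.** Five items match fully, pain Grade 3 is the same on both scales, and the card's swelling wording is the activity half of Appendix 2.
- **That the mismatch favours one arm.** Both blinded arms use the same card, the direction is mixed, and no formal test of reactogenicity is specified. What is affected is the reading of absolute rates.
- **That it undermines the dose choice.** Protocol Section 3.2.1 rests that decision on shedding, lesion rate, recurrence frequency and duration, and immunology, and mentions only a modestly higher Grade 3 frequency with more adjuvant. The 51.2% and 68.2% Grade 3 figures come from GEN-003-003, whose card is not shown.

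**What to change.** In SAP Table 14.3.1.7:

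1. Replace the two swelling rows with one grade per subject, derived from the two card fields by the Appendix 2 size-or-activity rule and taken at its maximum over the 7 days. Use that grade in the Any Local Reaction row. Keep the component values in Listing 16.2.7.2, which already has both columns.
2. Label the rows graded by the card as Diary Card grades.
3. Add a footnote that the card's 0-to-3 scores do not collect Grade 4, and that fever Grade 4 comes from temperature.

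In the protocol, reconcile Section 7.2.6, Appendix 2 and Appendix 3 so that one scale governs each solicited item. Which scale that should be is for the sponsor to settle.

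Pain and headache should not be regraded from medication records. The concomitant medication listing (16.2.4.4) has dates and route but no indication or dose times, so an analgesic cannot be tied to one symptom, nor repeated use beyond 24 hours established.

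The cost is one derivation, a shell change and footnotes, all on data already collected. The single swelling grade may not line up with parent-study tables if those used two rows, which is why the components stay in the listing.

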Appendix 4 Adverse Events of Special Interest

Gastrointestinal disorders

- Celiac disease
- Crohn's disease
- Ulcerative colitis
- Ulcerative proctitis

Liver disorders

- Autoimmune cholangitis
- Autoimmune hepatitis
- Primary biliary cirrhosis
- Primary sclerosing cholangitis

Metabolic diseases

- Addison's disease
- Autoimmune thyroiditis (including Hashimoto thyroiditis)
- Diabetes mellitus type I
- Grave's or Basedow's disease

Musculoskeletal disorders

- Antisynthetase syndrome
- Dermatomyositis
- Juvenile chronic arthritis (including Still's disease)
- Mixed connective tissue disorder
- Polymyalgia rheumatic
- Polymyositis
- Psoriatic arthropathy
- Relapsing polychondritis
- Rheumatoid arthritis
- Scleroderma (including diffuse systemic form and CREST syndrome)
- Spondyloarthritis (including ankylosing spondylitis, reactive arthritis [Reiter's Syndrome] and undifferentiated spondyloarthritis)
- Systemic lupus erythematosus
- Systemic sclerosis

Neuroinflammatory disorders

- Acute disseminated encephalomyelitis (including site-specific variants: e.g., noninfectious encephalitis, encephalomyelitis, myelitis, and myeloradiculomyelitis)
- Cranial nerve disorders, including paralyzes/paresis (e.g., Bell's palsy)
- Guillain-Barre syndrome (including Miller Fisher syndrome and other variants)
- Immune-mediated peripheral neuropathies and plexopathies (including chronic inflammatory demyelinating polyneuropathy, multifocal motor neuropathy, and polyneuropathies associated with monoclonal gammopathy)

- Multiple sclerosis
- Myasthenia gravis, including Eaton-Lambert syndrome
- Narcolepsy
- Optic neuritis
- Transverse myelitis

Skin disorders

- Alopecia areata
- Autoimmune bullous skin diseases (including pemphigus, pemphigoid, and dermatitis herpetiformis)
- Cutaneous lupus erythematosus
- Erythema nodosum
- Morphoea
- Lichen planus
- Psoriasis
- Sweet's syndrome
- Vitiligo

Vasculitides

- Large vessels vasculitis (including giant cell arteritis such as Takayasu's arteritis and temporal arteritis)
- Medium sized and/or small vessels vasculitis (including polyarteritis nodosa, Kawasaki's disease, microscopic polyangiitis, Wegener's granulomatosis, Churg-Strauss syndrome [allergic granulomatous angiitis], Buerger's disease [thromboangiitis obliterans], necrotizing vasculitis and antineutrophil cytoplasmic antibody positive vasculitis [type unspecified], Henoch-Schönlein purpura, Behcet's syndrome, and leukocytoclastic vasculitis)

Others

- Antiphospholipid syndrome
- Autoimmune hemolytic anemia
- Autoimmune glomerulonephritis (including immunoglobulin A nephropathy, glomerulonephritis rapidly progressive, membranous glomerulonephritis, membranoproliferative glomerulonephritis, and mesangioproliferative glomerulonephritis)
- Autoimmune myocarditis/cardiomyopathy
- Autoimmune thrombocytopenia
- Goodpasture syndrome
- Idiopathic pulmonary fibrosis
- Pernicious anemia
- Raynaud's phenomenon
- Sarcoidosis
- Sjogren's syndrome
- Stevens-Johnson syndrome
- Uveitis

Appendix 5 Genital Herpes Signs and Symptoms Diary

Genital Herpes Signs and Symptoms Diary
Version 5.0
January 17, 2017

Instructions to patients:
The following questions ask about signs and symptoms of your genital herpes. Signs of genital herpes may include having genital lesions (bumps, blisters, sores or scabs) that you may see or feel by touch, or drainage or swelling you might have from a genital lesion. These lesions may be on your genitals, genital area, thighs or buttocks.

Some people may experience certain symptoms with genital lesions including pain, itching, or pain with urination. Please read each question carefully and choose the one best answer for each question. Please consider any signs or symptoms due to your genital herpes at their **worst, in the last 24 hours**.

Q1: Do you have a genital herpes lesion (bump, blister, sore or scab) that you could see or feel by touch in the last 24 hours?
 Yes
 No

Q1a: If yes, approximately how many genital herpes lesions can you see or feel?
 1 2-4 5-7 8 or more

Q1b: (if patient answers “Yes” to Q1) Do you have an **open** genital herpes lesion (bump, blister, sore or scab)?
 Yes
 No

Q2: (if patients answers “No” to Q1) Did you experience any signs or symptoms in the last 24 hours that would indicate you will soon experience a genital herpes recurrence?
 Yes
 No

[Q3-Q4 asked ONLY if patient answers “YES” to Q1 or “YES” to Q2]
 [Q5-Q7 asked ONLY if patient answers “YES” to Q1]

Q3: Rate the severity of any itching you have experienced in the genital area over the last 24 hours

No itch										Worst possible itch
0	1	2	3	4	5	6	7	8	9	10

Q4: Rate the severity of any pain (soreness or tenderness) you have experienced in the genital area over the last 24 hours

No pain											Worst possible pain
0	1	2	3	4	5	6	7	8	9	10	

Q5: Rate the severity of any genital lesion pain during urination you have experienced over the last 24 hours

No pain with urination											Worst possible pain with urination
0	1	2	3	4	5	6	7	8	9	10	

Q6: Rate the severity of any genital lesion draining or discharge you have experienced over the last 24 hours

No draining or discharge											Worst possible draining or discharge
0	1	2	3	4	5	6	7	8	9	10	

Q7: Rate the severity of any genital lesion swelling you have experienced over the last 24 hours

No swelling											Worst possible swelling
0	1	2	3	4	5	6	7	8	9	10	

Section 7.2.2 - Medically Attended Adverse Events	A An MAAE is an AE resulting in hospitalization, emergency room visit, or visit to or from medical personnel (other than routine health care visits). If a MAAE is "hospitalization" it should be reported as an SAE as described in Section 7.6 below.	Typo Clarified reporting of MAAE that results in hospitalization.
Section 10.11 – Interim Analysis	Added: An interim analysis will be conducted after all viral shedding samples from Month 5 to 6 swab collection period have been tested and will include analysis of shedding and lesion rates. The specific contents of the interim analyses will be detailed in the SAP.	Added an interim analysis to the protocol.
Original 11.12 – Protocol Deviations	Deleted entire section.	Already included in Section 11.7.
Appendix 1	Subjects will report the presence or absence of genital lesions, severity of genital herpes symptoms, and the use of prescription medication to treat genital herpes on each day from Day 1 through Month 12.	Electronic diary will not capture daily use of antivirals.

Amendment 2, Protocol Version 2.0, 13 October 2017

The overall purpose of the amendment is to:

- Change clinical objectives and endpoint observation period from 12 months to 6 months
- Eliminate swab collection and shedding analyses
- Eliminate blood collection for immunology at Months 6 and 12, and eliminate immunology analyses
- Eliminate RGHQoL data collection, and analyses of all quality of life assessments
- Allow for use of suppressive antiviral medication following the Month 6 visit.

Summary of Changes

Section	Change	Rationale
Synopsis and Section 2.1.2 - Secondary Efficacy Objectives	
 • To evaluate the efficacy of GEN-003 versus placebo administered as a maintenance dose on genital herpes recurrence through 6 months: - Reduction of genital herpes recurrence frequency - Increase of proportion of subjects who are genital herpes recurrence-free at 12 months after the maintenance dose - Increase of time to first/next genital herpes recurrence - Reduction of genital herpes recurrence duration • To evaluate the efficacy of GEN-003 versus placebo administered as a maintenance dose in reduction of anogenital herpes simplex virus type 2 (HSV-2) shedding rates after the maintenance dose 	The Sponsor has stopped development of GEN-003 and therefore reduced collection and analyses of efficacy and viral shedding data
Synopsis and original Section 2.1.3 - Exploratory Objectives	Deleted entire section.	The Sponsor has stopped development of GEN-003 and therefore reduced collection and all analyses of viral shedding, immunogenicity, and quality of life data

Section	Change	Rationale
Synopsis and Section 3.1 - Overall Study Design, ¶2	Subjects will use a daily electronic tool for reporting the presence or absence of genital herpes lesions and the severity of genital herpes symptoms from Day 1 until the end of the study Month 6 Visit.	Modify design and procedures to reflect reduced data collection
¶3	Subjects will collect anogenital swabs for measurement of HSV-2 shedding twice a day for 28-day periods during Months 5 to 6 and Months 11 to 12. Samples will be analyzed for HSV-2 DNA by real-time quantitative polymerase chain reaction (PCR) assay.	
¶4	Subjects will complete the EuroQol – 5 Domains – 5 Levels (EQ-5D-5L) questionnaire on each day of the first recurrence after the maintenance dose through Month 6. and the Recurrent Genital Herpes Quality of Life Questionnaire (RGHQoL) at Month 6 and Month 12.	
¶5	A serum sample will be collected from each subject for evaluation of humoral responses future research purposes before the maintenance dose (Day 1), 7 and 28 days after the maintenance dose (Day 8 and Day 29/Month 1). and at Month 6 and Month 12. Immunoglobulin G (IgG) specific to the vaccine antigens will be measured by enzyme-linked immunosorbent assay (ELISA), and HSV-2 neutralizing antibodies will be measured by a colorimetric assay.	
¶6	At selected investigational sites, a whole blood sample will be collected and processed to isolate peripheral blood mononuclear cells (PBMCs) for evaluation of cellular responses future research purposes before the maintenance dose (Day 1), 7 and 28 days after the maintenance dose (Day 8 and Day 29/Month 1). and at Months 6 and 12. Secretion of granzyme B (GrB) and interferon-gamma (IFN-γ)	

Section	Change	Rationale
¶18	
specific to the vaccine-specific antigens will be measured by a GrB/IFN-γ FluoroSpot assay.
 
From Month 2 to Month 12, the investigational site will contact each subject monthly by telephone or site visit for review of daily electronic reporting tool data and assessment of SAEs, AESIs, and antiviral medication (through Month 6) and vaccine use.
	
Synopsis and Section 2.2.1 – Primary Efficacy Endpoint	
 Genital herpes lesion rate (proportion of days with lesions present) in the 42 6-month period after the maintenance dose: Based on subject report of genital lesions via a daily electronic reporting tool 	The Sponsor has stopped development of GEN-003 and therefore reduced collection and analyses of efficacy data
Synopsis and Section 2.2.2 – Secondary Efficacy Endpoints	
 Frequency of genital herpes recurrences in the 42 6-month period after the maintenance dose: Based on subject report of genital lesions via a daily electronic reporting tool Proportion of subjects genital herpes recurrence-free at 42 6 months after the maintenance dose: Based on subject report of genital lesions via a daily electronic reporting tool Time to first/next genital herpes recurrence in the 12 6-month period after the maintenance dose: Based on subject report of genital lesions via a daily electronic reporting tool Duration of genital herpes recurrences in the 12 6-month period after the maintenance dose: Based on subject report of genital lesions via a daily electronic reporting tool Anogenital HSV-2 shedding rates: Proportion of anogenital swabs positive for HSV-2 DNA by PCR after the maintenance dose 	The Sponsor has stopped development of GEN-003 and therefore reduced collection and analyses of efficacy and viral shedding data
Synopsis and original Section 2.2.3 – Exploratory Endpoints	Deleted entire section.	The Sponsor has stopped development of GEN-003 and therefore reduced collection and all analyses of viral shedding, immunogenicity, and quality of

Section	Change	Rationale
		life data

Section	Change	Rationale
Synopsis – Statistical Methods: Efficacy	
Genital herpes lesion rates (the proportion of days with genital lesions present) in the 12 6-month period after the maintenance dose will be compared between treatment groups using the Wilcoxon rank sum test. The frequency of genital herpes recurrences in the 12-month period after the maintenance dose will be calculated as the number of recurrences reported and summarized by mean, standard deviation (SD), median, and range. The median frequencies of recurrences in the 6-month period will be compared between treatment groups using the Wilcoxon rank sum test. The proportion of subjects in each treatment group who are genital herpes recurrence-free at 12 6 months after the maintenance dose will be tabulated and compared using a chi-square test for homogeneity of proportions. Time to first recurrence in the 12 6-month period after the maintenance dose will be tabulated and graphed using the Kaplan-Meier method. The log-rank test will be used to compare the time to first recurrence survival curves between the GEN-003 and placebo groups. Survival analysis with Cox model will be used to compare the time to next genital herpes recurrence. Duration of genital herpes recurrences over the 12-month period after the maintenance dose will be calculated and summarized by mean, SD, median, and range. Median of individual mean duration of genital herpes recurrences during the 6-month period will be compared using the Wilcoxon rank sum test. Deleted remainder of efficacy analysis methods.
	The Sponsor has stopped development of GEN-003 and therefore reduced analyses of efficacy data

Section	Change	Rationale

Section 3.2.2 – Efficacy Endpoints, ¶1, Sentence 1
 
¶2
	
Genital herpes lesion rate in the 12 6-month period after the maintenance dose was selected as the primary endpoint because lesion rate is the most comprehensive measure of genital herpes disease burden.
 
The secondary efficacy endpoints evaluate other clinically important measures of vaccine effect, such as the frequency and duration of genital herpes recurrences. In addition, the vaccine's ability to lower HSV-2 shedding rate will also be assessed. Viral shedding rate is a direct measurement of antiviral activity that has been used in previous studies of both vaccines and antiviral medications for genital herpes. It is an objective measure of antiviral activity against HSV-2.
	
To reflect change in primary endpoint observation period
 
To reflect that viral shedding will no longer be analyzed

Section 5.5 – Concomitant Medications, Sentence 2
	
Use of antiviral medications and vaccines will be recorded from Day 1 through the end of the study Month 6.
	
Collection of lesion data will end at Month 6, therefore subjects will be allowed to use antiviral medications following the Month 6 visit

Section 5.6.1.1 – Suppressive Therapy
	
Subjects are forbidden from taking suppressive antiviral therapy during this study through the Month 6 Visit.
	
Collection of lesion data will end at Month 6, therefore subjects will be allowed to use antiviral medications following the Month 6 visit

Section 5.6.1.1 – Treatment of Recurrences
	
Treatment of recurrences is NOT permitted during swab collection periods. Up to 3 days of antiviral treatment is permitted for recurrences that occur outside of swab collection periods.
	
Genital swabbing has been eliminated from the protocol

Section 5.6.2 - Medications and Supplements with Anti-HSV Activity
	
Use of acyclovir, valacyclovir, famciclovir, tenofovir (except for postexposure prophylaxis for HIV-1), lysine, or other medication or supplement known or purported to affect HSV recurrence frequency or intensity is prohibited from 14 days before the maintenance dose to the end of the study through the Month 6 Visit (except as noted in Section 5.6.1.2 for the acute treatment of genital herpes recurrences).
	
Collection of lesion data will end at Month 6, therefore subjects will be allowed to use antiviral medications following the Month 6 visit

Section	Change	Rationale
Original 5.6.3 – Topical Steroids and Antiviral Medications	Deleted entire section.	Genital swabbing has been eliminated from the protocol; section is irrelevant
Section 6.1 - Definitions and Descriptions of Assessments and Procedures, Daily Electronic Reporting Tool, sentence 3	Data must be entered daily through Month 6 Visit.	To reflect amended reporting period
Section 6.1 - Definitions and Descriptions of Assessments and Procedures, Anogenital Swabs and RGHQoL	Deleted	Genital swabbing and RGHQoL have been eliminated from the protocol
Section 6.1 - Definitions and Descriptions of Assessments and Procedures, EQ-5D-5L, sentence 1	The subject will complete this questionnaire on each day of the genital herpes first recurrence after the maintenance dose through Month 6.	To reflect amended reporting period
Section 6.2.1 – Day 1, ¶6	Upon determination that a subject meets all eligibility criteria, the following blood samples will be collected: - Serum for immunogenicity testing future research - At selected investigational sites: whole blood for PBMC isolation for immunogenicity testing future research	Immunogenicity testing has been eliminated from the protocol
Section 6.2.2 (Day 8), 6.2.3 (Day 29), original Section 6.3.4 (Months 6 and 12)	Sample collection: - Serum for immunogenicity testing future research - At selected investigational sites: whole blood for PBMC isolation for immunogenicity testing future research	Immunogenicity testing has been eliminated from the protocol
Section 6.3.1 – Follow-up Telephone Calls, ¶1 ¶2	Deleted Month 7 call The following procedures will be performed: • Review of daily reporting tool data (Month 4 only) • Assessment of SAEs, AESIs, and MAAEs • Assessment of antiviral medication and vaccine use through Month 6	No longer required Reflect new data collection periods

Section	Change	Rationale
Section 6.3.2 – Months 3 and 6	The following procedures will be performed: 
 • Review of daily electronic reporting tool data • Collection of completed EQ-5D-5L questionnaires, if completed • Assessment of SAEs, AESIs, and MAAEs • Assessment of antiviral medication and vaccine use The subject will be reminded to continue use of the daily electronic reporting tool.	Combined procedures for Months 3 and 6 (changed from 3 and 9) to reflect new data collection periods
Section 6.3.3 – Months 9 and 12	The following procedures will be performed: 
 • Assessment of SAEs, AESIs, and MAAEs 	Combined procedures for Months 9 and 12 (changed from 6 and 12) to reflect new data collection periods and elimination of blood sampling
Original Section 6.3.3 – Months 5 and 11	Deleted entire section	No longer required
Original Section 6.3.4 – Months 6 and 12	Deleted entire section and replaced with new section 6.3.3	See above
Section 10.4 – Subject Disposition, ¶3	Analysis populations will be summarized in a tabular format.	Data will be presented in listings only
Section 10.7 – Primary Efficacy Endpoint	Genital herpes lesion rates (the proportion of days with genital lesions present) in the 12 6-month period after the maintenance dose will be compared between treatment groups using the Wilcoxon rank sum test.	To reflect analysis of new observation period
Section 10.8.1 – Frequency of Genital Herpes Recurrences, sentence 1	The frequency of genital herpes recurrences in the 12 6-month period after the maintenance dose will be calculated as the number of recurrences reported and summarized by mean, SD, median, and range.	Reflect analysis of new observation period
Section 10.8.2 – Proportion of Subjects Recurrence-Free	The proportion of subjects in each treatment group who are genital herpes recurrence-free at 12 6 months after the maintenance dose will be tabulated and compared using a chi-square test for homogeneity of proportions.	Reflect analysis of new observation period

Section	Change	Rationale
Section 10.8.3 – Time to First Genital Herpes Recurrence	Time to first recurrence in the 12 6-month period after the maintenance dose will be tabulated and graphed using the Kaplan-Meier method. The log-rank test will be used to compare the time to first recurrence survival curves between the GEN 003 and placebo groups. Survival analysis with Cox model will be used to compare the time to next genital herpes recurrence.	Reflect analysis of new observation period; time to “next” recurrence will not be analyzed
Section 10.8.4 – Duration of Genital Herpes Recurrences, sentence 1	Duration of genital herpes recurrences over the 12 6-month period after the maintenance dose will be calculated and summarized by mean, SD, median, and range.	Reflect analysis of new observation period
Section 10.8.5 – Anogenital Shedding Rate	Deleted entire section	Genital swabbing has been eliminated from the protocol
